### **Protocol**

Oral informed consent was obtained from the eligible women at the initial interviews on the phone. The women who agreed to participate in the study were assigned to the groups according to the research randomizer software. The women assigned to experimental and control groups were planned first home visit and obtained written informed consent was obtained at this visits. At the Intervention group; the researcher made pretest (baseline measurements) before the nursing interventions at the first home visit. The researcher offered education and guide about prevention of lymphedema after the baseline measurements at the first home visit. Second and third home visits were made three and six months after the first visit. At the second and the third home visits, the measurements were repeated, and the nursing interventions were maintained in the direction of the patients' individual needs.

At the control group; the researcher administered the pretests at first home visit. The measurements were repeated in the third and sixth months after the first home visit. The

researcher also given at the end of the sixth month, all of the nursing interventions, given to the intervention group, for the control group.

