### **Intervention**

Education Material; Breast Cancer Related Lymphedema Education Guide, prepared in light of the literature and revised in accordance with three experts opinions, was used at home visits. The content of the guide was directed towards supporting seriousness and sensitivity of the participants about lymphedema and created by taking account of HBM.

Home Visits; At the first home visits to the intervention group, the researcher met the participants and their families, explained the aim of the study and administered the pretests. The guide was introduced, and health education was given. Arm exercises used to prevent lymphedema were demonstrated and measurement of the arm circumference was taught. Follow-up forms were introduced and from the women were asked to do exercises as daily, make measurements as weekly, and record them in the forms day to day regularly. The arm measurements made by the researcher were included into the analysis. The participants and their families were encouraged to phone and receive counseling about things which they needed. Each home visit lasted 45 minutes on average. Three and six months after the first visit, the patients were phoned and made an appointment. At the second and the third home visits, the measurements were repeated, and the nursing interventions were maintained in the direction of the patients' individual needs (repeated of education, exercises and arm circumference measurement, control of follow-up forms).

At the first home visits in the control group, the researcher was introduced herself, explained the study and administered the pretests. The measurements were repeated in the third and sixth months after the first home visit. The women in the control group were not told about the nursing interventions, given to the intervention group, during the study period in order to

avoid bias. At the end of the sixth month, education and guide about prevention of lymphedema were offered to this group.

Reminders; In the intervention group was sent a message reminding behavior preventing lymphedema every week.

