### **Statistical analysis plan**

Data obtained in this study were analyzed with SPSS 21.0. Multifactorial variance analysis of repeated measures was used to compare the groups in terms of dependent variables, the significance test of difference between two means to compare pretest and posttest measures, one-way variance analysis of repeated measures to compare intragroup pretest and posttest measures and t-test for dependent groups with Bonferroni correction to perform further analysis of the difference between the mean scores of the groups. Intention-to-treat (ITT) analysis was utilized to eliminate effects of dropouts from the study, to maintain randomization. To prevent bias the database were analyzed by a statistician who was independent of the study.

Costs of treatments likely to be given for lymphedema in the intervention group and the control group due to the potential incidence of this condition and HBM based nursing interventions to be offered at home visits were made. The costs of the nursing interventions included time spent by the researcher at home visits, transportation for these visits, reminders on the phone, education material and tape measure. The cost of treatment for lymphedema included costs of medical treatment of an individual with stage I/II lymphedema in upper extremities in hospital. It was based on opinions of three experts. To calculate the costs from the perspective of Social Security Institution, prices of services and materials reported in Health Services Bulletin issued in Mar 2017 were taken. The expenses directly made by the patients were determined by the mean value of prices obtained from three national firms.

[figure not shown]

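### The nursing-intervention cost list omits the on-demand phone counselling, and visit time is entered without separating research-only work, so the intervention cost needed for hypothesis 6 is misstated in an unknown net direction

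*Combined protocol and SAP*

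**What the plan says.** The cost paragraph of the Statistical analysis plan says the nursing-intervention costs included "time spent by the researcher at home visits, transportation for these visits, reminders on the phone, education material and tape measure". A separate item covers hospital treatment of lymphedema.

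The Intervention section describes more contact with the researcher than that list names:

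- **Phone counselling.** "The participants and their families were encouraged to phone and receive counseling about things which they needed".
- **Reminders**, under their own label: "In the intervention group was sent a message reminding behavior preventing lymphedema every week".
- **Visits.** "Each home visit lasted 45 minutes on average". The Protocol section sets the number at three: "Second and third home visits were made three and six months after the first visit".
- **Content of visit 1.** The researcher "explained the aim of the study and administered the pretests", then introduced the guide, taught and demonstrated. The Protocol section adds written consent.
- **Content of visits 2 and 3.** "At the second and the third home visits, the measurements were repeated, and the nursing interventions were maintained", with the intervention part spelled out as "repeated of education, exercises and arm circumference measurement, control of follow-up forms".

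Control women had the same measurement schedule. They were offered the education and guide at the end of month six. Hypothesis 6 is that mean cost is lower in the intervention group.

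**The concern.** The cost of an intervention should cover what was delivered because of it, and nothing that both groups received only because they were in a study. The list departs from the first rule and may depart from the second.

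The counselling calls take staff time and are offered to the intervention group only, so leaving them out makes the intervention look cheaper. Consent, study explanation and questionnaires would not form part of a home-visit service, and the control group had them as well. If they sit inside the priced visit time, the intervention looks dearer.

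Hypothesis 6 and the closing statement that home-visit follow-up is cost-effective both need a sound cost of delivery. A reader given only a total from this list could not tell how far it is off, or in which direction.

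**Working it through.** **Step 1: match the delivered components to the cost list.**

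| Component described in Intervention or Protocol | In the cost list? |
|---|---|
| Researcher time at home visits | Yes, not split by activity |
| Travel to visits | Yes |
| Weekly reminder messages | Yes |
| Education guide | Yes |
| Tape measure | Yes |
| Counselling calls from women and families | No |

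The phone item in the list is reminders. The Intervention section describes reminders as weekly messages sent to the women, whereas counselling runs the other way, on calls made by the women or their families. The reminder item therefore does not cover counselling.

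**Step 2: what the priced visit time contains.** Written consent and the study explanation fall at visit 1, and the outcome measurements fall at all three visits. From the Study outcomes section, the three scales have 11 (Q-DASH) + 29 (SUPPH) + 23 (QLQ-BR23) = 63 items. There is also a 17-question personal information form. All of this is research-only. Arm circumference measurement is different: it was taught at visit 1 and is named among the interventions at visits 2 and 3, so it belongs in the intervention cost.

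**Step 3: the documents' own figures.** Visit time per intervention woman = 3 visits x 45 min = 135 min. The only cost result tied to hypothesis 6 is the fourfold lower lymphedema treatment cost, given under Ethical aspects. It cannot be reproduced, because no unit prices or lymphedema counts are given. None of the listed nursing items enters it.

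**Step 4: direction of the two effects.** Delivered intervention time per woman is

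T = 3 x (45 - m) + c x d,

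where m is the average research-only minutes per visit, c the calls per woman over six months and d the minutes per call. The documents give none of these three. The values below are assumptions that show direction and are not estimates.

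| Assumed case | T (min) | T / 135 |
|---|---|---|
| List taken whole: m = 0, c = 0 | 135 | 100% |
| Calls only: c = 1, d = 10 | 135 + 10 = 145 | 107% |
| Calls only: c = 6, d = 10 | 135 + 60 = 195 | 144% |
| Research time only: m = 10 | 135 - 30 = 105 | 78% |
| Research time only: m = 25 | 135 - 75 = 60 | 44% |
| Both: m = 25, c = 1, d = 10 | 135 - 75 + 10 = 70 | 52% |
| Both: m = 10, c = 6, d = 10 | 135 - 30 + 60 = 165 | 122% |
| Both: m = 10, c = 3, d = 10 | 135 - 30 + 30 = 135 | 100% |

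The two effects cancel whenever c x d = 3m. Under plausible inputs the net error can take either sign or be nil. These are shares of visit minutes, not of cost: travel, materials and reminders lie outside the 135.

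**The case against.** The other side has five arguments.

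- **The list may not be exhaustive.** It is introduced by a verb that allows for other items. That is true, but a list detailed enough to name a tape measure gives no reason to assume that an open-ended item of staff time was priced silently.
- **Uptake of calls is unknown.** Women were encouraged to phone, and perhaps few did. This stands. It limits what can be said about size but does not excuse the missing item.
- **The plan never says that research time was priced.** This also stands. A reader might infer that all 45 minutes of every visit were wrongly charged to the intervention. The documents do not support that as a fact: they list visit time without a split and do not say whether any was excluded. A reader might also class arm measurement as research-only, which the Intervention section contradicts.
- **Counting research time is conservative.** It raises the intervention cost and so works against hypothesis 6. That is correct for this part alone. It does not offset the missing calls by any known amount.
- **The reported confirmation of hypothesis 6 uses treatment cost only.** This stands, and it means that no effect of the list on the stated conclusion has been shown. A reader might infer that the conclusion would be reversed; nothing in the documents supports that. But a cost-effectiveness statement about home visits needs the cost of delivering them, and the list is the only source for it.

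**Conclusion.** The point holds in two parts of unequal strength.

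The omission is plain from the text. Phone counselling is part of the intervention and is absent from the cost list, so a cost built from that list understates what was delivered, in favour of hypothesis 6.

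The treatment of visit time is a gap. The plan does not separate consent, study explanation and questionnaires from intervention work. If they were priced, the cost is overstated. With both in play, the net direction is unknown.

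Beyond 135 visit minutes per woman, the documents give nothing from which to compute the size. The range of 70 to 165 minutes with both corrections rests wholly on assumed values: 10 to 25 research-only minutes per visit and 1 to 6 calls of 10 minutes. The matter bears on the cost hypothesis and the cost-effectiveness statement, not on the clinical outcomes.

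**What to change.** In the cost paragraph of the Statistical analysis plan:

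1. Add researcher time and call charges for counselling calls from participants and families to the intervention cost.
2. Count only intervention time at visits. Exclude consent, study explanation and questionnaires; keep the arm measurement that the Intervention section lists as intervention. Report the minutes and call counts used.
3. Do not obtain intervention time by subtracting the control group's month-6 visit length. Controls were offered the education and guide at the end of month six, so the subtraction could remove genuine intervention time. The documents also give no control visit length.
4. If calls or visit minutes were not logged, report total cost (nursing plus treatment) by group over a stated range of calls and research-only minutes per woman. Say whether the sign of the group difference changes within that range.
5. State that this total is the quantity that tests hypothesis 6.

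The cost is one reworked cost table or a short sensitivity table, with no new patient data. The cost difference may turn out less favourable to the intervention.

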**13.07.2017**

## **Background**

Secondary lymphedema is one of the most severe complications resulting from damage to lymphatic drainage due to breast cancer treatment. Many women suffer from lymphedema after breast cancer treatment. Due to the lack of standard diagnostic criteria for the incidence of lymphedema varies from less than 5% to more than 50%. In a recent meta-analysis, it has been found to be 21.4%.

The primary risk factors of lymphedema are lymph node involvement and axillary lymph node dissection. The other risk factors are radiotherapy, adjuvant chemotherapy, early postoperative swelling, body mass index, advanced age, insufficient physical activity, infections in the affected arm and injuries. A study performed axillary dissection in women with breast cancer and found that 13.4% of the women not receiving radiotherapy and 42.4% of the women receiving radiotherapy had lymphedema.

Lymphedema reduces the quality of life due to physical and psychosocial disorders it creates. Women with lymphedema have physical problems such as restricted movements, retraction, weakness, pain and swelling on the affected breast and arm, difficulty in maintaining daily life activities and psychological problems like low self-confidence, disappointment, sadness and fear due to the appearance of lymphedema.

It has been reported that the yearly cost of treatment (visits to therapists and compression garment) per person is \$977 for lymphedema, \$277 for subclinical lymphedema, higher than \$1400 for moderate and severe lymphedema. Effective management of lymphedema on the affected arm could reduce negative effects of lymphedema and resultant high treatment costs.

Nurses believed that risk reduction (95%) and self-management (68%) were the responsibility of nursing while 69% felt that management of lymphedema was the responsibility of a different discipline, such as lymphedema therapy. The patient-centered educational and behavioral program delivered by trained nurses is effective to enhance lymphedema risk reduction. Lewis and Morgan emphasized that cooperation with public health nurses improves

patient care outcomes and costs associated with lymphedema management. At this point, the literature suggested that nurses should inform individuals about the risk of lymphedema after breast cancer.

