### **Study outcomes**

Personal Information Questionnaire;The questionnaire, developed by the researchers, is composed of 17 questions about sociodemographic characteristics, diagnosis and treatment of breast cancer, behavior of lymphedema prevention.

Quick-Disabilities of the Arm, Shoulder and Hand Score;Q-DASH is used to determine severities of disabilities in the upper extremities and benefits gained from treatment. It was adapted...by Duger et al. and its cronbach's alpha was reported to be .91. It is a five-point likert scale and includes 11 questions. The score zero indicates lack of a disability and 100 the most severe disability.

Strategies Used by Patients to Promote Health;SUPPH is a self-report scale created by Lev and Owen to evaluate self-efficacy of individuals in development of health promotion strategies. It was adapted by Akin and its Cronbach's alpha was reported to be .92. The scale consists of 29 items. The subscale stress reduction includes the items 1-10, making decision the items 11-13, positive attitude the items 14. Each item is scored from one to five:one corresponds to very little and five very much. The lowest and the highest scores for the scale are 29 and 145 respectively. Higher scores show higher levels of self-efficacy in self-care behavior 29.

European Organization for Research and Treatment of Cancer Quality of Life Scale for Breast Cancer 23;EORTC QLQ-BR23 was developed from European Organization for Research and Treatment of Cancer Quality of Life Scale 30 by EORTC to measure the quality of life in individuals with breast cancer. It was adapted Turkish by Demirci et al. The scale is composed of 23 items, a four-point scale and has two scales named FS and SS. Cronbach's alpha was reported to be .88 for the FS .66 for the SS. The FS has the subscales body image (items 39,40,41,42), sexual functions (items 44,45), sexual satisfaction (item 46), worry about the future (item 43). The SS has the subscales side effects of systematic treatment (items 31,32,33,34,36,37,38), breast symptoms (items 50,51,52,53), arm symptoms (items 47,48,49), worry about hair loss (item 35). The lowest and the highest scores for each scale are zero and

100 respectfully. Higher scores for the FS show a higher quality of life and higher scores for the SS indicate a poorer quality of life.

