To calculate scores for the FS and the SS, the total score for the items of each scale is divided by the total number of items and the following formulae are used:  $FS = \{1 - (((\text{total score for the items}) / \text{number of items}) - 1) / \text{range}\} \times 100$  and  $SS = \{(((\text{total score for the items}) / \text{number of items}) - 1) / \text{range}\} \times 100$ . The highest and lowest score for the items are four and one and the difference between them, that is, three, refers to range.

Arm Circumference Measurement Form; The form was made on four different sites on both arms: at the dorsum of the hand, the wrist, and 10cm below and above of the elbow. The difference more than 2cm between circumferences of the arms was considered as significant in terms of lymphedema.

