### **Ethical aspects**

Ethical approval was obtained from DEU Noninterventional Clinical Research Committee (Protocol number: 2014/08-19; approval number: 248; date: 4 April 2013 970-GOA) and State Hospitals Directorate. Oral informed consent was obtained from the women at the initial

interviews on the phone and written informed consent was obtained at the first home visits. At the end of the study, nursing interventions about prevention of lymphedema were offered to the control group.

In the current study, the HBM based nursing interventions offered at home visits decreased perceived barriers to lymphedema management, increased perceived benefits and improved self-efficacy in positive health behavior.

The cost of treatment for lymphedema in the intervention group was four times as low as that in the control group, which confirmed the sixth hypothesis. The finding indicated that follow-up of women having breast surgery through home visits is a cost-effective practice. Programs conducted in cooperation with public health nurses improve patient care outcomes and reduce costs for lymphedema. Sixty-seven percent of the women mention the presence of a financial burden of breast cancer treatment and 80% of the women point out to the cost of treatment for lymphedema. Treatment of breast cancer costs \$14.887-23.167 in patients developing lymphedema after breast surgery than those without lymphedema and this complication increases indirect costs due to loss of work force.

Abbreviations: EORTC QLQ-BR23, European Organization for Research and Treatment of Cancer Quality of Life Scale for Breast Cancer 23; SUPPH, Strategies Used by Patients to Promote Health; Q-DASH, Quick-Disabilities of the Arm, Shoulder and Hand Score.

**FIGURE** Consort flowchart

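### The four-fold treatment-cost ratio appears to be the lymphedema case ratio restated, and the saving per woman behind the cost-effectiveness conclusion rests on an unverified price with no interval

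*Combined protocol and SAP*

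**What the plan says.** **Costing (Statistical analysis plan).** The quantity costed is "Costs of treatments likely to be given for lymphedema in the intervention group and the control group due to the potential incidence of this condition". The price basis is "The cost of treatment for lymphedema included costs of medical treatment of an individual with stage I/II lymphedema in upper extremities in hospital", and "It was based on opinions of three experts". Service prices come from a March 2017 bulletin, and patients' own expenses from three firms. The section also lists programme costs: researcher time, transport, phone reminders, education material and tape measure. The readable text gives no amount for any of these.

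**Case definition (Study outcomes).** "The form was made on four different sites on both arms", and "The difference more than 2cm between circumferences of the arms was considered as significant in terms of lymphedema". No stage is assigned. The personal questionnaire "is composed of 17 questions about sociodemographic characteristics, diagnosis and treatment of breast cancer, behavior of lymphedema prevention"; lymphedema treatment is not among the topics named.

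**Hypotheses.** Hypothesis 5 concerns lymphedema incidence. Hypothesis 6 concerns mean cost at home visits.

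**Conclusion (closing text under Ethical aspects).** "The cost of treatment for lymphedema in the intervention group was four times as low as that in the control group". This is said to confirm hypothesis 6 and to show that home visits are cost-effective. No case count, unit price or interval accompanies it.

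**The concern.** A cost result supports an economic conclusion only if it holds information about cost. Here the route from a case to money appears to be one expert-set price for a hospital-treated stage I/II patient. It is applied to women identified by a tape-measure difference that shows neither stage nor treatment. Two consequences follow.

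- The treatment-cost ratio would repeat the incidence comparison in other units, so presenting it as confirming a further hypothesis counts one finding twice.
- Whether the programme pays for itself depends on the absolute saving per woman set against programme cost. That saving depends fully on a price and a treated share that the trial is not described as checking.

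A bare point ratio answers neither question and conceals how few events may lie behind it.

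**Working it through.** **Inputs from the document**
- Group sizes: 37 intervention and 35 control (Sample size calculation). The Randomization section says 100 per group. The two must be reconciled; 37 and 35 are used here.
- Reported treatment-cost ratio, control to intervention: 4 (Ethical aspects).
- Background yearly costs: $277 subclinical, $977 lymphedema, more than $1400 moderate or severe. These cover therapist visits and compression garments and are not the trial's prices. They serve only as illustrative weights.

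**Assumptions**
- Case counts are not in the readable text, and a figure is not shown. The pairs below are chosen to give about a four-fold ratio.
- One price *c* per case, and a share *s* of cases treated, the same in both arms.

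**Step 1: the reported ratio.** It cannot be reproduced, because no counts or prices are given. Its structure can be shown. With *a* intervention cases and *b* control cases:

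total-cost ratio = (c × s × b) / (c × s × a) = b / a

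Price and treated share cancel. For 2 v 8 cases the ratio is 8/2 = 4.0 on totals, and (8/35)/(2/37) = 0.2286/0.0541 = 4.23 per woman. Both hold at $277, $977 or $1400.

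**Step 2: precision of the ratio.** The standard error of the log ratio is √(1/a − 1/37 + 1/b − 1/35). For 2 v 8 it is 0.755, so the limits are 4.23 × exp(±1.96 × 0.755).

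| Assumed cases (intervention v control) | Per-woman ratio | 95% CI | Fisher p |
|---|---|---|---|
| 1 v 4 | 4.23 | 0.50 to 36.0 | 0.19 |
| 2 v 8 | 4.23 | 0.96 to 18.6 | 0.043 |
| 3 v 12 | 4.23 | 1.30 to 13.7 | 0.009 |
| 4 v 16 | 4.23 | 1.57 to 11.4 | 0.001 |

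The same headline ratio can be weak or strong evidence, depending on counts that are not shown.

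**Step 3: the saving per woman.** Saving = c × s × (b/35 − a/37). For 2 v 8 the risk difference is 0.2286 − 0.0541 = 0.1745.
- All cases treated: 277 × 0.1745 = $48; 977 × 0.1745 = $171; 1400 × 0.1745 = $244.
- Half of cases treated in each arm, at $977: $85, with the ratio still 4.23.
- At $977 with all treated, a Newcombe 95% interval for the risk difference (0.011 to 0.341) gives about $11 to $333 per woman.

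**Step 4: net of programme cost.** With programme cost *K* per intervention woman (an assumption, as no amount is given), the net saving is the Step 3 saving minus *K*. For 2 v 8 at $977, break-even is therefore *K* = $171. The control-to-intervention ratio of total cost is (977 × 8/35) / (977 × 2/37 + K), which is 2.17 at *K* = $50, 1.46 at $100 and 0.88 at $200. The four-fold treatment-cost ratio is the same in all three cases.

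**Step 5: what could move the ratio.** Only differences between arms in severity, treatment or case finding, or misclassification of cases. For 2 v 8, intervention cases at $277 and control cases at $977 would give 14.9; the reverse would give 1.2. False positives at 5% or 10%, equal in both arms, would lower 4.23 to 2.64 or 2.06.

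**The case against.** The strongest objections are these.

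- **The price does not inflate the ratio.** A reader might infer that charging every case a hospital course exaggerates the four-fold figure. It does not: a common price cancels (Step 1). The document states no absolute saving for the trial either, so there is no reported amount to call inflated. This stands. What remains exposed is the cost-effectiveness conclusion, which needs that amount.
- **Hypothesis 6 is wider than hypothesis 5.** A reader might infer that hypothesis 6 as a whole is redundant. The plan does not support that: it also costs the programme, so a full comparison would not be a rescaled case count. Only the treatment-cost component derives from hypothesis 5. But the ratio offered as confirmation is treatment cost alone.
- **One price per case is inferred.** The document never states the multiplication, and the stage I/II sentence says only what was included. This stands as a caveat. No other treatment package is described.
- **The background dollar range is not the trial's.** The roughly five-fold spread ($1400/$277 = 5.1) describes another type of care, and nothing shows that cases above 2 cm are subclinical. From the general lymphedema figure upward, the spread is $1400/$977 = 1.4. The five-fold figure is therefore not a bound on error.
- **Events may not be few.** Participants had axillary dissection and radiotherapy, for which the Background cites 42.4%. Applied to 35 controls that is about 15 (0.424 × 35 = 14.8), although follow-up may differ. The 4 v 16 pair is then nearer than 1 v 4, and its interval excludes 1. A claim that the result rests on a handful of cases is not supported; the claim that its precision is unstated is.
- **Modelling is a legitimate, disclosed choice.** The methods text says so openly. The closing text does not carry that qualification forward.

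**Conclusion.** The point holds in a limited form. On the reading that each case carries one price, the four-fold ratio is the case ratio and adds no cost evidence beyond hypothesis 5. The saving per woman is proportional to an unverified price and to the share of cases treated. In the assumed 2 v 8 example it is $48 to $244 across the background prices, and it halves if half the cases are treated. Depending on the assumed counts, the lower 95% limit of the ratio lies anywhere from 0.5 to 1.6. These sizes rest on assumed case pairs, on groups of 37 and 35, and on illustrative prices. The documents do not show that the ratio is inflated, that events were few, or that the programme fails to save money. They do show that the stated result is not sufficient to confirm hypothesis 6 or to support the cost-effectiveness conclusion.

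**What to change.** In the Statistical analysis plan and the closing text under Ethical aspects:

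1. Label treatment cost as modelled, and state the number of cases above 2 cm in each arm, the unit price, and whether every case received that price.
2. Replace the statements that hypothesis 6 was confirmed and that home visits are cost-effective with a cost difference per woman that includes the programme costs already listed. Carry the confidence interval of the case difference into it.
3. Add a sensitivity analysis over unit price and share of cases treated. Because stage is not described as recorded, vary these as scenarios; the Background severity figures may serve as relative weights only.
4. State that the treatment-cost component derives from hypothesis 5 and is not independent support.
5. Reconcile 100 per group (Randomization) with 37 and 35 (Sample size calculation), since the interval depends on it.

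This needs no new data if case counts, the unit price and programme costs are on file. The cost is a few extra calculations, some rewording, and a saving that will look less favourable and visibly uncertain.
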